
## **Follow-up Assessment Notification**

About a month before the start of the follow-up surveys (T2 in 2020 and T3 in May 2021), teachers will send a notice home with consented students who participated in the Baseline (T1) survey informing them and their parents of another survey coming. The study staff will follow the same procedures outlined for the baseline assessment of the students.

### Parent/guardian survey.

There are four methodologies for completing the parent/guardian survey.

1. From the consented family, the parent completed the baseline survey and is available to complete the FU survey.
2. From the consented family, the parent consented, but did not complete the baseline survey. They will be invited to complete the follow-up survey.
3. From the consented family, the parent completed the baseline survey but is unable to complete the FU survey at any time in the follow-up window (T2 is April-May 2020).
4. A 3rd or 4th grader or their family are requesting an opportunity to participate at follow-up but have not yet completed the family packet or consent or assented their child.

1. The assessment coordinator will contact the parent who completed the baseline (the index parent/guardian) to again participate in the follow-up surveys (T2, and later T3).
2. The assessment coordinator will contact the parent who consented to the baseline but did not complete the survey (the index parent/guardian), to participate in the follow-up surveys (T2, and later T3).
3. If it is found that the index parent/guardian is not able to complete the survey, a new index parent/guardian can be appointed. The new index parent/guardian will be contacted to complete *Parent Survey and Verbal Participation Consent Form* approved by IRB. The verbal consent will be read and must be verbally affirmed by the parent/guardian prior to completing the parent survey interview. At the top of the parent follow up survey, there is a space for the interviewer to note change in survey completer.

**New Student Enrollment:** New students will not be actively recruited to participate in the study at T2 or T3. If the new student or their parent wishes to participate on their own accord, they can request an enrollment packet from their teacher. In this way, students enrolled at a participating school in the 3rd or 4th grade after the baseline assessment was completed will have the opportunity to participate in the assessment. The first step is for them to take home the enrollment packet for their parent/guardian to complete. The child cannot participate in the survey without a completed packet. As before, the packet will include information about the study, child assent and adult caregiver permission and self-consent to participate in the study, and a Parent Family Survey (all documents IRB approved – see section VI List of Approved Documents). The student and parent/guardian must complete the enrollment documents and return the sealed packet to the teacher. The teacher will give the sealed packets to the school designated school champion to be securely locked in the assessment file cabinet until retrieved by the study staff. Procedures for obtaining student follow-up survey and parent follow-up survey will follow similar steps to those used at the baseline survey.

## CONTEXT

New Mexico and Arizona State have mandated closure of all schools for the duration of the school year in response to slowing COVID-19 spread. The study has had to revise its protocol for obtaining the primary outcome measure that includes student follow-up assessment in April/May 2020.

## Student Follow-up Assessment (amended due to COVID-19)

### Preparation

Yéego! Healthy Eating & Gardening project has mailing addresses (including PO Box numbers) for almost all of the 3rd and 4th grade students in all six schools. For those students for whom the study has no address, contact will be made via phone and email requesting mailing address. It is anticipated that we will obtain mailing addresses that will reach ALL the 3rd and 4th grade students.

In addition to the mailed survey, parents/guardians that provided email addresses will be sent an email with a secure link to the follow-up survey. The weblink will send participants to a new virtual server with more restrictive access. The Yeego Server and the process to protect the files stored locally at Fred Hutch was approved by Information Security Office and IRB 08-12-2019.

### Awareness communication plan

- Text blast/robocall: Yéego! staff will work with the principals of the enrolled schools for permission to use the teacher text blast or robocall system currently in place at the school. Text blast/robocall will be sent only to enrolled 3rd and 4th graders. The text blast/robocall will alert the student's parent/guardian that Yéego! staff will be in contact by email and/or phone regarding the follow up survey.

### Individual Communication to provide tailored link and survey modality choice

- Email push: The Nutrition Assessment Shared Resources (NASR) will generate a standard email with a unique/personalized participant log-in link so students and parents/guardians can complete the follow-up survey online. 96% of parents/guardians provided an email when enrolling into the study.

- Text/Phone: The data collection team will contact participants by phone or text at the number provided on the Family Survey during enrollment. The call will take place after the text blast/robocall to participants and the email push. The purpose of the call is to determine the best modality for administering the survey. Prior to the phone call, the data collector will check to confirm whether an online survey has been completed. The data collector will let the participant know they can complete the survey online, by mail or by phone. The call could lead to a phone survey completion.

#### Follow-up survey delivery

- Online: The participant can complete the survey online. The Yeego study will be adding the capacity to collect online follow-up data directly from participants. An additional virtual server has been set up to host follow-up questionnaires. Data transmission from the participant to the questionnaire site will be encrypted via transport layer security (TLS). The questionnaire server will send participant responses to the encrypted study database, which is hosted on a separate server that is not accessible outside the Hutch network. Participants will be sent a participant-specific link by email. The link will direct them to the follow-up questionnaires. There is no personally identifying information presented or requested in the follow-up questionnaires.
- Mail: A packet will be sent to the mailing address provided. It will contain a cover letter, student/child survey with face sheet, parent/guardian survey with face sheet), and a return postage-paid envelope.

Note: For a household where the parent/guardian did NOT complete a baseline survey, no parent follow-up survey will be included.

The assessment goal is to get as many of the original students and parent/guardians who completed baseline survey to complete the follow-up survey. In order to achieve a high response rate, the cover letter will include a phone number for the student/parent guardian to call if they prefer to conduct the interview over the phone, and an email to request a web-link if the student/parent guardian prefers to complete the survey online. The cover letter will also include a description of the incentives for completing the survey(s).

- Phone: The parent/guardian of the child will be contacted by phone (see individual communication and modality above). The parent can choose to have the child complete the interview over the phone at that time with a data collector, or can schedule a more convenient time to complete the survey by phone. The student/child survey and parent survey participants can use the hardcopy mailed survey as a guide for the phone interview.

#### Non-responder calls:

Two weeks after the initial mailing, non-responders will be contacted by phone to confirm they received the mailed packet, and to check their preferred modality for completing the survey (paper, phone or online). Once this preference is communicated (via mail, phone or email) with the study interviewer, they will arrange a time with the student (and the parent/guardian for the subset completing parent surveys) to complete the survey over the phone. The student can use the paper survey as a guide.

Note: For those participants without phone numbers, a second mailing will be sent two weeks after the original mailing.

### **C.     Outcome Measures**

The primary outcomes for this randomized controlled trial are differences in changes from T1 to T2 in healthy eating behaviors and gardening participation and self-efficacy in the **children** from the intervention school relative to the **children** from the delayed intervention school(s). Assessments are restricted to 3rd and 4th grade because of greater reliability among children aged 8 or older.

**Child Healthy Eating Behaviors.** Tendency to Choose Fruit and Vegetables to Eat, Assessing dietary intake in elementary school age children is notoriously difficult. Different simple approaches to approximating choices or eating behaviors have been attempted, including use of self-efficacy scales. Questions using

a 4 point Likert scale were modified from two other studies of children, using 5-point and 3-point Likert scales. Seven questions ranging from “At lunch, I usually choose to eat vegetables, such as celery sticks or carrots” to a reverse code of “During snack time, I usually choose to eat cookies or crackers” are combined and averaged for an overall score. In a recent study in children, the scores ranged from 1.14 to 3.86, with an average of 2.44 (s.d. =0.48). **Healthy Eating Score**. We will use the picture sort method developed in our current study, which allows us to estimate the frequency of eating foods that comprise ten major food groupings of the Navajo diet, including breads; vegetables and salad; fruits; beverages; soups or stews; cereals; dairy and eggs; rice, pasta etc; meat, chicken or fish; and desserts and snacks. Sufficient detail within the broad groupings was retained to allow estimation of six of the eleven components of the AHEI. Elements of the index that we were able to include are vegetables, fruits, whole grains, nuts and legumes, as well as sugar sweetened beverages and fruit juice, and red/processed meat. Trans fat, long chain fats, PUFA, sodium and alcohol will not be assessed in the children. The resulting Healthy Eating Score has a range of possible values from 0 to 47, and in our current study, the mean score was 14.6.

**Child Gardening Participation and Self-efficacy**. **Gardening at Home**. We will ask children if they have a garden at home, and if so how often they do gardening activities there. Responses had good variability in our current study – just over half reported affirmatively for “like to garden” and “have a place to garden” (Table 3). The analytic variable used will be proportion reporting gardening at home at least sometimes. **Gardening self-efficacy**. Self-efficacy questions regarding how confident they are in their ability to perform the behaviors come from the LA Sprouts studies. The measures were evaluated for validity and reproducibility in schools in the Los Angeles area. The self-efficacy variable used in the analysis will be a combined six-item likert scale.

**Parent dietary behaviors**. Dietary intake questions include fruit and vegetable consumption using an instrument used in the 5 a Day study, as well as soda and fast food consumption. This set of obesity related dietary behaviors will be combined into an index ([name] & [name], personal communication). The parent will also complete the virtual picture sort frequency method following the approach used in our current study (originally developed in an African American community and modified for this study using foods commonly consumed by Navajo). Again, the weekly frequencies will be converted to a relative healthy food ratio (healthy foods to total foods) for the parent, based on AHEI categories.

**Parent gardening behaviors**. Our parent gardening frequency measure assesses typical frequency of gardening per week in the past three months, which we have adapted and modified from our previous studies to date. We will also ask about the presence of a garden at the home, frequency of participation in any gardening in the child’s school or, if applicable, their home garden. Additional questions concerning degree of familiarity about what is being planted/grown/harvested in the school garden will be included.

**Intermediate outcomes**. For children, these include determinants of dietary behavior consistent with the approach used in the *LA Sprouts study*, and the vegetable intake, food security and family relationships measures used in the *Community Gardening Project in Oregon*. Gardening capability questions will be developed for children to indicate how well they know how to do specific gardening tasks that are taught in the curriculum (e.g. planting, weeding, watering, harvesting). We will also assess the participation of the students in the school garden, and the adoption by the students of positive attitudes towards growing vegetables, fruits and making healthy food choices.

#### **D. Process Measures: Recruitment, Retention and Fidelity**

We will assess recruitment, retention and fidelity using logs, tracking forms and checklists kept by the Project and Intervention Coordinators. We will also take minutes at all meetings with project staff, school staff and community advisors where recruitment, retention, reach, participant satisfaction, and fidelity will be regularly discussed. Recruitment. Data collectors will document the number of participants approached and recruited into the study in both the intervention and delayed intervention comparison group. Retention. Data collectors will document the number of eligible participants that complete each assessment. Intervention Fidelity. We will use checklists to assess fidelity to the intervention protocol during lessons.

Teacher/Interventionist Checklist: Teachers will complete checklists at the end of each lesson to gauge fidelity of curriculum implementation. Based on previously outlined session themes and activities, instructors will report to what degree session specific content was addressed. Instructors will also be asked to comment on

session materials and preparation, noting things that inhibited or facilitated their ability to deliver program content, or any variation in participation. Observer Checklist: A data collector will be present at each lesson to complete an observation checklist, reporting the degree to which the intervention protocol is followed. This will include monitoring attendance, level of participation/exposure, content covered, and session logistics including materials provided and degree of preparation. Data collectors will also note barriers and facilitators to participation and engagement in session activities. Data from the checklists will be analyzed to assess fidelity to the intervention protocol.

## E. Analysis Plan

Two of our four primary outcome measures in children (tendency to choose fruit and vegetables to eat during snacks/meals and gardening self-efficacy) will be measured through questions that use a Likert-type scale with four response options. With numeric codes assigned to each response option, means and standard deviations will be calculated per question and overall. Thus, possible mean values range from one to four. The intention to treat analysis will be a t-test comparing the change in mean values from baseline (beginning of school year at T1) to follow-up (end of school year at T2) in the intervention schools to those changes in mean values in the schools receiving the delayed intervention. This differential change in groups between T1 and T2 is the estimated intervention effect. The estimated effect of the intervention will also be analyzed using linear mixed models with T2 individual outcome as the dependent variable and intervention assignment as the

independent variable, adjusting for T1 individual outcome and school random effect. It will also allow for adjustment for additional covariates (school within intervention group if applicable) and for known or probable individual level confounders. Information from all responding students will be included in the analysis, with adjustment for repeated measures (expected to be the majority of the students). This will assess robustness of inferences from the simpler model. A sensitivity analysis without adjusting for possible intra-school correlations will be performed using linear regression models. In addition, the Akaike Information Criterion will be compared between the simpler model and the theoretically correct multilevel model to check model fit.

The picture sort method uses references to 26 commonly consumed food items by Navajo chosen to represent six of the broad food components captured within the AHEI, and four other Navajo food groups. Frequency of consuming foods from each group, with specific focus on the six AHEI relevant components will be estimated and compared across schools. The healthy components are fruits, vegetables, whole grains, and nuts and legumes, and the so-called “unhealthy” components based on AHEI scoring are sugar-sweetened beverages and fruit juice, and red/processed meat. Differential change in the derived healthy eating score will be estimated, and evaluated using a t-test, conservatively, assuming a Normal distribution for the score, based on the Central Limit Theorem. Similarly, the proportion of children who participate in gardening at home will be calculated for each school, and the differential change estimated and evaluated using a z-test for proportions.

Secondary outcomes, including those collected from the parents of participating children, will be analyzed similarly. Mean values and standard deviations for scored variables will be calculated, and intervention effects estimated, and evaluated using t-tests. Frequencies will be estimated for categorical outcomes and intervention associated differences in frequency distributions across categories will be evaluated using Pearson's Chi-square test. Since both parent and child data will be collected, parent-child pairs will be created and explored, including the use of generalized mixed models to account for within-family correlations. The form of dyad analysis used will take into account that the members of the dyad are distinguishable.

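### The tests named for the four primary outcomes do not carry through the promised adjustment for school clustering, and the plan contradicts itself on which analysis is primary

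*Combined protocol and SAP*

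**What the plan says.** Sections III.A and III.D randomise whole schools within Shiprock and Tsaile. With six schools, two receive the intervention and four the delayed intervention. The amended student follow-up text in IV.B refers to six schools, so 2 vs 4 is the live case. The Specific Aims (II) say that the analyses of the intervention effect will adjust for clustering by school.

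Section IV.E then sets out:

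- **Tendency to choose fruit and vegetables, and gardening self-efficacy.** "The intention to treat analysis will be a t-test comparing the change in mean values from baseline" to follow-up in the intervention schools with "those changes in mean values in the schools receiving the delayed intervention".
- **Mixed model.** A linear mixed model for the T2 outcome is fitted as well, "adjusting for T1 individual outcome and school random effect". Its stated purpose: "This will assess robustness of inferences from the simpler model".
- **Unadjusted regression.** "A sensitivity analysis without adjusting for possible intra-school correlations will be performed using linear regression models".
- **Model fit.** The Akaike criterion is compared between "the simpler model and the theoretically correct multilevel model to check model fit".
- **Healthy eating score.** Differential change is "evaluated using a t-test, conservatively, assuming a Normal distribution for the score, based on the Central Limit Theorem".
- **Gardening at home.** A proportion is calculated per school, and the differential change is assessed with a z-test for proportions.

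None of the four named tests has a stated unit, df or cluster term. IV.E does not say whether the mixed model extends to the last two outcomes.

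**The concern.** Children in one school share teachers, meals and a garden, so their changes may be correlated. With six randomised units, a test that counts children as independent overstates the information.

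The plan also leaves the ranking of its analyses unresolved. One sentence makes the plain t-test the main analysis and the multilevel model its check. Another calls the unadjusted regression the sensitivity analysis, which implies that the adjusted one is main. A third calls the multilevel model the theoretically correct one. Two analysts could follow this text and report very different intervals from the same data. The trial is meant to estimate efficacy and to support a larger proposal (V.D), so the estimate and its uncertainty are its product.

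**Working it through.** The documents give no power calculation, alpha or intra-school correlation (ICC), so there is no figure of the plan's own to reproduce. I assume two-sided 5% and an ICC of the T1-T2 change of 0.01, 0.02 or 0.05.

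**Inputs.** Six schools, 2 vs 4, one intervention and two delayed schools per community (III.A, III.D). Children per school: 40-100 pupils in grades 3 and 4 (III.D) × the 60% enrolment goal (IV.B) = 24 to 60. Losses at T2 would lower these numbers and the errors below.

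**1. Child-level t-test, all correlation at school level.** Design effect DE = 1 + (m − 1) × ICC. True error = 2 × [1 − Φ(1.96/√DE)].

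| m | ICC | DE | Error |
|---|---|---|---|
| 24 | 0.01 | 1.23 | 7.7% |
| 24 | 0.02 | 1.46 | 10.5% |
| 24 | 0.05 | 2.15 | 18.1% |
| 60 | 0.01 | 1.59 | 12.0% |
| 60 | 0.02 | 2.18 | 18.4% |
| 60 | 0.05 | 3.95 | 32.4% |

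At ICC 0.001 the error is 5-6%. Simulation of the child-level t-test agrees within about one percentage point.

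**2. The same test when communities differ.** Each arm takes half its schools from each community, so community effects cancel from the contrast. If half the between-school variance lies between communities, the variance ratio becomes (1 − ICC) + m × ICC/2:

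- m = 24: 0.99 + 0.12 = 1.11, 0.98 + 0.24 = 1.22 and 0.95 + 0.60 = 1.55, giving errors of 6.3%, 7.6% and 11.5%.
- m = 60: 0.99 + 0.30 = 1.29, 0.98 + 0.60 = 1.58 and 0.95 + 1.50 = 2.45, giving errors of 8.4%, 11.9% and 21.1%.

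The step 1 figures are therefore upper values at each ICC.

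**3. School-level t-test.** With six school means, df = 6 − 2 = 4 and the critical value is 2.776. With equal school sizes and no community variance, the error is 5%. With half the between-school variance between communities, simulation gives 3.3-4.5% (slightly conservative). Adding community as a stratum leaves 3 df (critical value 3.182) and restores about 5%.

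**4. z-test for gardening at home.** There are two ways to build it.

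- *School-level statistic referred to 1.96:* P(|t₄| > 1.96) = 12.2%, or about 8.5-11% with the community variance of step 2.
- *Binomial variance from children:* if the variance uses the T1-T2 pairing, the errors are those of steps 1 and 2. If T1 and T2 are treated as independent, which IV.E leaves open, the ratio of true to assumed variance is (1 − r) × DE, where r is the within-child correlation. For r between 0.7 and 0.3 (assumed), it runs from 0.3 × 1.23 = 0.37 to 0.7 × 3.95 = 2.77. The error runs from 0.1% to 24%, so it can go either way.

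**5. Mixed model with a plain Wald z.** Simulated for 2 vs 4, m = 24-60 and ICC 0.01-0.05, the error is 5.3-11.1%. The school variance is estimated at zero in 8-48% of trials. The model therefore also needs a small-sample df method.

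**6. Interval width.** Ratio to the naive interval = 2.776 × √DE / 1.96. Smallest: 2.776 × √1.23 / 1.96 = 1.57. Largest: 2.776 × √3.95 / 1.96 = 2.82.

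**The case against.** The strongest reply is that clustering has not been overlooked. The Aims promise adjustment without limiting it to some outcomes, IV.E specifies a school random effect, and it labels the unadjusted regression as sensitivity. A reader might infer that the plan ignores clustering; the documents do not support that. What remains is that the named tests do not show the adjustment, the ranking contradicts itself, and no cluster model is named for two of the four primary outcomes.

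Secondly, the t-tests may be meant at school level, which the wording about means in the schools allows. They would then be about right, but a z reference for gardening at home would not.

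Thirdly, a reader might infer that no reading of the plan can give valid tests. That is too strong. It requires schools to vary in their change, and at ICC 0.001 the child-level t-test is nearly correct. Likewise, 12% belongs to one construction of the z-test. A conventional z-test for proportions uses binomial variance from children, so 12% should not be quoted as the error of the named test.

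Finally, this is a small trial, with formal evaluation deferred to a later proposal (V.D), and no alpha is stated. Interval width is then the more relevant harm, but the same correction is needed.

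**Conclusion.** Wrong as written. The tests named for the four primary outcomes do not deliver the promised adjustment, and IV.E gives conflicting signals about which analysis is primary. If schools vary in their T1-T2 change, an unadjusted child-level t-test understates uncertainty. A z-test for proportions has the wrong error under either construction, although treating T1 and T2 as independent can make it too cautious. School-level t-tests would be about right.

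The size is illustrative because the ICC is assumed. For ICC 0.01 to 0.05, child-level t-test error is about 8-18% at 24 children per school and 12-32% at 60 when all correlation is at school level. It is about 6-12% and 8-21% when half the between-school variance is between communities. The contradiction in the ranking and the missing unit and df rest on the text alone and need no ICC.

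**What to change.** In IV.E, make one cluster-respecting, T1-adjusted analysis primary for all four outcomes.

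- **Default:** a two-sided school-level t-test on T1-adjusted school means or proportions. Use 4 df for 2 vs 4 (slightly conservative if communities differ), or 3 df with community as the randomisation stratum, and state which.
- **School sizes:** state the weighting. In simulation without community variance, the unweighted 4-df test stays near 5% with equal or mixed sizes. It ranges from about 3% to 9% when the arms differ strongly in school size (24 against 60 children). Weighting by size with a pre-stated ICC of 0.01 or 0.02 narrows this to about 4-6.5%.
- **Alternative:** the mixed model already in IV.E, extended to all four outcomes and in a form suited to yes/no data for gardening at home. Name a small-sample df method and a rule for a school variance estimated at zero; do not use a Wald z.

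Replace the z-test for gardening at home accordingly and apply the same principle to the secondary outcomes. Keep the plain t-, z- and chi-square tests as sensitivity or descriptive analyses, and reword the robustness and sensitivity sentences to give one ranking.

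The cost is plan wording and minor programming, with no new data. Intervals become about 1.6-2.8 times the naive width (2 vs 4, ICC 0.01-0.05, 4 df), and the plan should say so. With 3 df the multiplier is 3.182 rather than 2.776, about 15% wider for the same standard error.
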